This primary analysis will be performed in the cocci-positive per-protocol population of subjects who meet the case definition of coccidioidomycosis pneumonia and who were adherent to the intervention administration (See Section 11.4.1). As defined below, adherence will be defined as taking at least 80% of the study medication (fluconazole or placebo) as determined at the day 22 visit. Pill count, if available, will take precedence over patient report of adherence.

Case Definition

The case definition of coccidioidomycosis pneumonia is met if the is subject diagnosed with CAP at the time of enrollment as determined by the referring health care provider, and meets one of the following serologic criteria:

1. The patient is positive for any two serologic tests at any time point from Day 1 through Day 29. The two positive results can but do not necessarily have to be from the same assay or the same time point. The assays considered for this criteria are: Immunodiffusion testing [IDTP (IgM) and IDCF (IgG)]; Enzyme linked immunoassay testing (EIA-IgM and EIA-IgG); OR
2. The patient is negative for anti-*Coccidioides* antibody by immunodiffusion assay (or EIA-IgG) at Day 1 and sero convert to positive for anti-*Coccidioides* antibody by immunodiffusion assay (or EIA-IgG) at any time point after Day 1 through Day 29; OR
3. The patient is negative or indeterminate for anti-*Coccidioides* antibody by CF assay on Day 1 and demonstrates a titer of greater than or equal to 2 by CF assay at any point after Day 1 through Day 29; OR
4. The patient is positive for anti-*Coccidioides* antibody by CF assay on Day 1 and demonstrates a rise of greater than or equal to 2-fold dilution in Complement Fixation (CF) titer compared to baseline at any time point after Day 1 through Day 29.

All serologic testing for a single participant from Day 1 through Day 29 will be batched and run concurrently to eliminate confounding due to test run variability.

Adherence

Adherence in all subjects will be assessed by patient self-report and pill count according to standard procedures, on Days 22, 29 and 43. Pill count, if available, will take precedence over patient report. If pill count is not available, patient report will be used.

To be considered adherent at a visit when the clinical response is measured, the subjects will need to have taken at least 80% of their expected pills.

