5.3.3.1. Discontinuation from Treatment

In addition, a subject will be discontinued from the active treatment and continue to be followed if the subject meets any of the following reasons:

- If any of the following criteria for liver-related adverse events are met and confirmed:
 - AST elevation of >5X ULN or greater than or equal to 225 IU/L or
 - ALT elevation of >5X ULN or greater than or equal to 250 IU/L or
 - Total bilirubin elevation >1.5X ULN or
 - Aminotransferase elevation of >3X ULN accompanied by total bilirubin elevation >1.5X ULN
- If any subject experiences any of the following:
 - QTc prolongation as defined by a corrected QT of > 500ms OR > 60ms above baseline measurement
 - Torsades de pointes (torsades, TdP)
 - Unexplained Syncope
 - Seizure in non-epileptic patients
- Medical disease or condition, or any new clinical findings that meet an exclusion criterion or for which continued participation, in the opinion of the site principal investigator or appropriate sub-investigator, would compromise the safety of the subject, would interfere with the subject's successful completion of the study, or would interfere with the evaluation of responses.
- A SAE as defined in the protocol. The subject will be followed until the resolution of the event.

-
- Pregnancy. The subject will be followed up to two months after delivery.
 - New information becomes available that makes further participation unsafe or no longer in the best interest of the subject.
 - Diagnosis of disseminated coccidioidomycosis.
 - Subsequent hospitalization for this CAP episode occurring greater than 72 hours after study randomization.
 - Worsening oxygenation: need for assisted ventilation including continuous positive airway pressure (CPAP), bilevel positive airway pressure (BIPAP), or mechanical ventilation.
 - Unable to adhere to scheduled study visits (e.g. relocation at a distance from the study center that precludes adherence)
 - Determined by a physician's discretion to require additional therapy not indicated in the protocol to ensure his/her health and well-being.

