5.3.4. Handling of Withdrawals and Discontinuation of Administration

The primary reason for withdrawal from the study will be recorded on the Study Status data collection form. Subjects will be encouraged to complete the Early Termination Visit. The Early Termination Visit procedures are listed in Section 7.6. Although subjects are free to withdraw at any time or may be withdrawn by the site principal investigator or appropriate sub-investigator at any time, subjects who receive at least one dose of the study drug will be encouraged to remain in the study for follow-up safety assessments and collection of clinical outcome data. Every attempt will be made to follow all serious adverse events ongoing at the time of early withdrawal to resolution.

In the case of subjects who fail to appear for a follow-up safety assessment, extensive effort (i.e., three documented contact attempts via phone calls, e-mails, etc., made on separate occasions and

followed by a certified letter) will be made to locate or recall them, or at least to determine their health status. These efforts will be documented in the subject's records.

See the appropriate section of the Manual of Procedures (MOP) for alternate follow-up requirements.

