6.7. Rescue Procedures

Subjects who meet any of the following criteria will be removed from the treatment arm, informed of their treatment assignment, and referred to a healthcare provider for continuing of care.

1. Subsequent hospitalization for this CAP episode occurring greater than 72 hours after study randomization.
2. Worsening oxygenation: need for assisted ventilation including continuous positive airway pressure (CPAP), bilevel positive airway pressure (BIPAP), or mechanical ventilation.
3. Determined by a physician's discretion to require additional therapy not indicated in the protocol to ensure his/her health and well-being

After a subject meets one of these criteria, they will be referred back to the health care provider. All available coccidioidal serologic results will be made available to the subject. All participants will be invited to remain in study follow-up. Participants who discontinue treatment due to rescue therapy may be eligible to participate in another study for an alternative coccidioidomycosis pneumonia treatment.

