7.4. Early Termination Visit (if needed)

7.4.1. Before Follow-up Visit 04

The following assessments will be performed at the early termination visit for subjects who withdraw, or are withdrawn or terminated from this study:

- Obtain interim medical/surgical history, including an assessment for new medical conditions and symptoms by interview of subjects and review of the medical record and note any changes since the previous visit.
- Record all concomitant medications on the appropriate data collection form.
- Assess any SAEs and record on SAE form and in AdvantageEDC.
- Complete a targeted physical examination based on symptoms.
- Record vital sign measurements (sitting blood pressure, sitting heart rate, respiratory rate, oral temperature, oxygen saturation and weight).
- Perform urine pregnancy test for women of child-bearing potential.
- Perform a 12-lead ECG if termination occurs before Day 15
- Perform a pill count of study product (fluconazole or placebo) and interview to determine adherence. Following pill count, collect the pill bottle and retain until study product accountability has been completed by the study monitor.
- Complete symptom Assessment including FLEET CAP Score, PROMIS Item Bank v2.0 - Ability to Participate in Social Roles and Activities - Short Form 4a, Extra-Pulmonary Symptom Score and SF-12v2
- Collect the number of days missed from school and/or work due to illness for subjects who were either enrolled in school or employed at baseline.
- Draw venous blood samples for the following:

-
- Safety laboratories (Hepatic function panel (AST, ALT, Alkaline phosphatase and total bilirubin), BUN, Creatinine) [10 mL]
 - Coccidioidal serologies (CF; qualitative IDCF and IDTP; EIA-IgM; EIA IgG; and quantitative IDCF) [15 mL]
 - Quantitative fluconazole level [5 mL]
 - Blood to be banked for future use [15 mL]
 - Contact subject with results of the safety lab testing for follow-up with health care provider if abnormalities are noted.
 - All available coccidioidal serologic results will be made available to the subject. The treatment status will be revealed to the participant. All participants will be invited to remain in study follow-up. Refer subject to their identified health care provider.

7.4.2. After Follow-up Visit 04 A telephone visit will be conducted.

The following assessments will be performed at the early termination visit for subjects who withdraw, or are withdrawn or terminated from this study:

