11.4. Final Analysis Plan

11.4.1. Analysis Populations

Safety Analyses:

- Safety population – This safety analysis population includes all subjects who took at least one dose of study medication.

Efficacy Analyses:

- Intent-to-Treat (ITT) population – This efficacy analysis population includes all randomized subjects.
- Cocci Positive Modified Intent-to-Treat (mITT) population – This efficacy analysis population includes all randomized subjects who meet the case definition of coccidioidomycosis pneumonia and took at least one dose of study medication. Note that it is not necessary for a subject to be adherent to study drug to be eligible for inclusion in the mITT population.
- All Randomized Modified Intent-to-Treat (mITT) population – This efficacy analysis population includes all randomized subjects who took at least one dose of study medication regardless of cocci-status. Note that it is not necessary for a subject to be adherent to study drug to be eligible for inclusion in the mITT population.

- Cocci Positive Per-Protocol (PP) population – This efficacy analysis population includes randomized subjects who meet the case definition of coccidioidomycosis pneumonia who were compliant with the intervention administration and have coccidioidal serology data available at the Day 1 and 22 visits.
- All Randomized Per-Protocol (PP) population – This efficacy analysis population includes randomized subjects who were compliant with the intervention administration regardless of cocci-status and have coccidioidal serology data available at the Day 1 and 22 visits.

Adherence is assessed at each study visit depending on the fraction of expected pills taken on or before that time point. If at any visit the subject's cumulative fraction of pills taken drops below 80%, they are deemed non-adherent. This decision is not reversible, even if the subject's cumulative fraction of pills taken rises above 80% at a future visit.

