From that visit forward in time, the subject is dropped from the PP analysis populations, and their data after that visit is censored from time to event analysis, and they are dropped from any fixed time point analyses occurring after that visit. Data collected from time points prior to the time point at which a subject becomes non-compliant will still contribute to efficacy analyses. In the unlikely event of an error in randomization or drug distribution, subjects will be grouped by the study product they actually received in the per-protocol and safety analyses, but will be grouped by their intended randomized assignment in the intent-to-treat and modified intent-to-treat analysis.

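### As written, the primary per-protocol analysis can exclude, rather than count as failures, cocci-positive subjects who died before the Day 22 sample or whose study drug was stopped early for worsening disease

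*Combined protocol and SAP*

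**What the plan says.** **Primary set.** Section 11.4.4.1 places the primary comparison in the cocci-positive PP population. Section 11.4.1 limits that set to subjects with "coccidioidomycosis pneumonia who were compliant with the intervention administration and have coccidioidal serology data available at the Day 1 and 22 visits".

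**Adherence.** Section 3.2.1 defines it as "taking at least 80% of the study medication (fluconazole or placebo) as determined at the day 22 visit". Section 11.4.1 judges it by the "fraction of expected pills taken on or before that time point" and makes a fall below 80% irreversible: "From that visit forward in time, the subject is dropped from the PP analysis populations".

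**Mandated stops.** Section 5.3.3.1 stops drug for, among other reasons, "Subsequent hospitalization for this CAP episode occurring greater than 72 hours after study randomization", assisted ventilation and disseminated coccidioidomycosis. The first two are also rescue criteria in Section 6.7, under which subjects "will be removed from the treatment arm, informed of their treatment assignment, and referred to a healthcare provider". Section 5.3.4 says subjects who have had at least one dose are "encouraged to remain in the study for follow-up safety assessments and collection of clinical outcome data".

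**Failure coding.** Section 11.4.4.1 codes subjects without a Day 22 response as treatment failures. For cocci-positive drop-outs, Section 11.2.1 states non-responder imputation only for the secondary mITT and ITT analyses. Section 11.4.4.1 says that sensitivity analyses for drop-out may be performed and leaves them to a separate SAP, which is not among the documents.

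**The concern.** Restricting the primary analysis to adherent subjects is the stated objective (Section 3.1.1) and is not disputed. The gap is narrower. Some cases become non-adherent because the protocol itself stopped their drug when the pneumonia worsened or spread, and some die. These are among the worst outcomes the trial can observe, and the primary denominator can lose them. No section exempts them from the pill or serology conditions.

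If the share removed differs by arm, the PP difference is no longer the difference that would be seen with these subjects counted as failures. Section 11.4.4.1 plans a by-arm comparison for selection into the primary analysis through case diagnosis. It plans no specific by-arm comparison for selection through pills or missing serology. Section 9.2.2 calls death part of the efficacy endpoints, yet the response definition in Section 3.2.1 gives it no role, and mortality is only a descriptive secondary outcome (Table 11). These passages need reconciling.

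**Working it through.** **1. The plan's own figures.** Unpooled Z test, two-sided 0.05: power = Φ(d/SE − 1.96), with SE = √[p₁(1−p₁)/n₁ + p₂(1−p₂)/n₂].
- Section 11.2.1 primary: 0.20 vs 0.40, 100 per arm. SE = √(0.0016 + 0.0024) = 0.0632; 0.20/0.0632 = 3.16; power 88.5% (stated 88%).
- Section 11.2.1 mITT: 0.16 vs 0.32, 125 per arm. Power 85.4% (stated 85%).

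**2. Who fails the pill rule.** Section 7.3.1 has the day's dose taken before the count, so a visit on Day d expects d daily doses if counting runs to the visit. The Day 22 window is Day 20 to 23.
- Day 20: 16 needed (15/20 = 75.0% fails)
- Day 21: 17 (16/21 = 76.2% fails)
- Day 22: 18 (17/22 = 77.3% fails)
- Day 23: 19 (18/23 = 78.3% fails)

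So a case stopped with fewer than 16 to 19 doses is dropped. If expected pills instead stop accruing at the stop date, the case can stay in but, if stopped under Section 6.7, is scored after being told the assignment. The text does not say which applies.

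**3. Who fails the serology rule.** Criterion 1 of the case definition can be met by two positive results on the Day 1 sample alone. Such a subject who dies before the Day 22 sample is a case but cannot enter the PP set, whatever the pill count.

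**4. Size under assumed exclusions.** The documents give no rates, so let eP and eF be the assumed shares of cases removed on placebo and fluconazole, all of them failures. Keep the design's PP rates (0.20, 0.40) and hold the PP set at 200, as Sections 11.2.1 and 11.3.3 intend:
- cases per arm M = 200/[(1−eP) + (1−eF)]
- PP size per arm = M(1−e)
- rates with the removed subjects restored as failures: 0.20(1−eP) and 0.40(1−eF)

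The PP difference is 20.0 points in every row.

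| eP / eF | Restored rates | Restored difference (points) | M | PP power | Power with failures restored |
|---|---|---|---|---|---|
| 10% / 5% | 0.180 vs 0.380 | 20.0 | 108.1 | 88.7% | 91.9% |
| 15% / 5% | 0.170 vs 0.380 | 21.0 | 111.1 | 88.8% | 95.0% |
| 20% / 5% | 0.160 vs 0.380 | 22.0 | 114.3 | 88.8% | 97.2% |
| 5% / 2% | 0.190 vs 0.392 | 20.2 | 103.6 | 88.6% | 90.7% |
| 5% / 5% | 0.190 vs 0.380 | 19.0 | 105.3 | 88.5% | 87.8% |
| 2% / 5% | 0.196 vs 0.380 | 18.4 | 103.6 | 88.4% | 84.8% |
| 5% / 10% | 0.190 vs 0.360 | 17.0 | 108.1 | 88.3% | 81.4% |
| 5% / 15% | 0.190 vs 0.340 | 15.0 | 111.1 | 88.1% | 72.9% |
| 5% / 20% | 0.190 vs 0.320 | 13.0 | 114.3 | 87.8% | 62.6% |

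The restored difference is 0.20 + 0.20eP − 0.40eF, so it equals the PP difference when eP = 2eF. With equal shares it shrinks slightly only because both rates are scaled down; the ratio stays at 2. The ratio 2(1−eF)/(1−eP) falls below 2 only when the fluconazole share is the larger.

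**5. Price of restoring them.** With an equal share r in both arms, rates are 0.20(1−r) and 0.40(1−r).
- Added on top of 100 adherent per arm, n = 100/(1−r), about 105, 111 and 125 for r = 5, 10 and 20%: power 87.8, 87.0 and 85.4%.
- Counted toward the 200, n = 100: power 86.1, 83.3 and 76.9%.

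**The case against.** **The mITT already counts them.** The cocci-positive mITT needs only one dose, treats drop-outs before Day 22 as non-responders and has 85% power. This largely stands for deaths and for subjects who leave. It is only a partial check: rescued subjects who accept the invitation to stay are scored on a symptom scale after learning their assignment. It is also secondary, so it does not correct the primary test.

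**Sensitivity analyses are foreseen.** They are, but only as an option, in an SAP that cannot be consulted here. The point therefore concerns the protocol text, and that SAP may close part of the gap.

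**The pill limb depends on a reading.** It does. Section 11.4.1 also drops non-adherers from fixed time point analyses occurring after the visit, which could be read as keeping Day 22 itself. The wording that drops them from that visit forward, together with Section 3.2.1, points to exclusion. The serology limb needs no such reading.

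**Restoring only failures changes the target.** True, and it is a named downside of the fix.

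**Stronger readings.** A reader might infer that the PP test overstates fluconazole's benefit, by up to 7 points in the last row of the table. That row needs a drug that doubles response among adherers yet produces four times the placebo share of worsening stops or deaths, and nothing in the documents supports this. A reader might also infer an inflated type I error. That needs unequal removal despite equal overall response; with equal rates and equal shares there is none, and the documents give no arm-specific shares.

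**Conclusion.** The point holds as a gap in the primary analysis rule. Exclusion is certain for cases who die before the Day 22 sample. For early mandated stops it is conditional on counting expected pills to the visit.

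Neither direction nor size can be established from the documents; every exclusion share above is an assumption. If an effective drug means fewer worsening stops, placebo shares of 10 to 20% against 5% understate the difference by 0 to 2 points. Material overstatement arises only if more fluconazole failures are removed. Small shares matter little: 5% vs 2% gives 20.2 points against 20.0. The larger assumed shares would use up most or all of the 20% drop-out that Section 11.2.1 allows for. PP power is 87.8 to 88.8% in every scenario, so the stated power is not in question; what the primary estimate represents is.

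This should be fixed, with medium confidence, because the remedy is cheap and the primary analysis should say how its worst outcomes count.

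**What to change.** In Sections 11.4.1 and 11.4.4.1, keep the 80% rule and add one exception. A subject who meets the case definition on available serology, and who would otherwise leave the PP set because by the Day 22 visit they died, were diagnosed with disseminated disease, or had drug stopped for CAP hospitalisation or assisted ventilation, is included in the primary analysis as a treatment failure. Subjects who remain adherent with a Day 22 score keep that score. Stops at a physician's discretion go to a sensitivity analysis.

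Also:
- define expected pills as counted to the visit;
- use the same coding in the conditional-power calculation (Section 11.3.2);
- add these subjects on top of the 200 adherent cases, so they do not count toward the enrolment target;
- make the drop-out sensitivity analysis mandatory;
- report PP exclusions by arm and reason, including liver and QTc stops, which the recoding does not cover.

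**Cost.** Protocol and SAP wording and one more table; no new visits or assays. Outcome follow-up after stopping is already encouraged, and the early termination visit already draws serology. Power falls from 88.5% to 87.8, 87.0 or 85.4% with equal recoding of 5, 10 or 20%. The primary set is no longer purely adherent subjects.

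**Limits.** A subject with no sample after Day 1 is recoverable only if Day 1 serology alone meets the case definition. A subject rescued late but still adherent keeps a score taken after disclosure. The change concerns analysis coding only; no clinical rule is altered.

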3.1.2. Secondary

- To assess the clinical response of early empiric antifungal therapy with fluconazole at Day 22 in subjects with coccidioidomycosis pneumonia regardless of adherence with the study intervention.
- To assess the clinical response of early empiric antifungal therapy with fluconazole at Day 43 in subjects with coccidioidomycosis pneumonia regardless of adherence with the study intervention.
- To compare the clinical response and its individual components over time, by treatment group, in subjects with coccidioidomycosis pneumonia.
- To assess the impact of early empiric antifungal therapy with fluconazole on days lost from work or school and responses to the SF-12v2 and PROMIS Item Bank v2.0 - Ability to Participate in Social Roles and Activities - Short Form 4a in subjects with coccidioidomycosis pneumonia.
- To assess the effect of early empiric antifungal therapy with fluconazole through Day 43 in subjects with coccidioidomycosis pneumonia on all-cause mortality by treatment group.
- To assess whether early empiric antifungal therapy with fluconazole at Day 22 is non-inferior to placebo as defined by clinical response at Day 22 in all randomized subjects, regardless of coccidioidomycosis pneumonia status or adherence with study intervention, with baseline and follow-up FLEET-CAP scores.

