11.2. Sample Size Considerations

11.2.1. Sample Size for Per Protocol Analysis Population

The primary analysis will compare the proportion of subjects achieving clinical response at Day 22 among efficacy evaluable subjects, defined as subjects in the Cocci-Positive Per Protocol analysis population who meet the case definition of coccidioidomycosis pneumonia who were compliant with the intervention administration and have coccidioidal serology data available at the Day 1 and 22 visits. We further assume that the clinical response proportion at Day 22 will be 0.20 in the placebo arm, and 0.40 in the fluconazole arm. As described in section 11.2.3, enrollment will continue until 200 subjects are evaluable for efficacy, 100 in each treatment arm, which suffices for 88% power for the Z test with unpooled variance to compare proportion of clinical responses at Day 22 at the two-sided level of 0.05. This is the primary sample size calculation which forms the basis for target enrollment to the study and for subsequent sample size re-estimation procedures at scheduled interim analyses while the study is enrolling.

A secondary analysis in the Cocci Positive Modified Intent-to-Treat population will compare the proportion of responders at Day 22, treating subjects dropping out before the Day 22 visit as non-responders. Assuming that the probability of drop-out before Day 22 is 20% among cocci-positive subjects, we would expect that 250 cocci-positive subjects would be available for this secondary analysis as a result of reaching the target sample size of 200 cocci-positive subjects with Day 22 follow-up for the primary analysis. Since subjects who drop-out are considered non-responders, the probability of response in the control-arm subjects would be $0.8 * 0.2 = 0.16$, and in the treated subjects would be $0.8 * 0.4 = 0.32$. The Z-test with unpooled variance has power of 85% to detect this difference in response proportions with 125 cocci-positive subjects per arm.

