11.4.4.1. Primary Efficacy Analysis

The primary efficacy analysis tests the difference between the fluconazole and placebo treatment groups in the proportion of subjects with an occurrence of clinical response at Day 22. Subjects without a clinical response at Day 22 will be coded as treatment failures while subjects with a clinical response at Day 22 will be coded as an observed event if the clinical response outcome measure definition (Section 3.2.1) is met.

A test of difference between the proportion of clinical responses in the fluconazole and placebo groups at the Day 22 time point will be performed using the Z test. The use of this test statistic will permit us to use the method of B-values to calculate conditional power of the test in the planned futility analyses, as outlined in “Statistical Monitoring of Clinical Trials, a Unified Approach”, by Proschan et al [22]. Details of this procedure will be provided in the statistical analysis plan.

The primary efficacy analysis will be performed in the cocci-positive per protocol analysis population. Secondary analyses will be performed in the all randomized per protocol population, all randomized and cocci-positive ITT and the mITT populations (see also Secondary Objectives 1 and 6). Sensitivity analyses, which will assess the impact of drop-out, censoring mechanisms, and analysis methods on the primary analysis, may be performed. These analyses will be specified in the separate statistical analysis plan document.

In addition to the planned tests of hypotheses, descriptive analyses will be performed for the primary endpoint. The number of clinical responses observed will be tabulated by time point, including and beyond Day 22, and treatment group. Tabular and graphical summaries will be prepared for the composite MSG score across all assessment time points.

To investigate whether there is evidence of a differential diagnosis of coccidioidomycosis between treatment arms, which might result in selection bias for inclusion in our primary analysis, the number of coccidioidomycosis cases in each treatment arm will be compared among all randomized subjects.

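### The per-protocol definitions require a Day 22 serum that case status does not need, and omit the Day 22 FLEET CAP score that the primary endpoint does need

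*Combined protocol and SAP*

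**What the plan says.** **Population definitions.** Section 11.4.1 limits the Cocci Positive Per-Protocol (PP) set, on which the primary analysis runs, to cases "who were compliant with the intervention administration and have coccidioidal serology data available at the Day 1 and 22 visits". Section 11.2.1 defines efficacy-evaluable subjects in the same way: "compliant with the intervention administration and have coccidioidal serology data available at the Day 1 and 22 visits". The All Randomized PP set takes compliant subjects "regardless of cocci-status and have coccidioidal serology data available at the Day 1 and 22 visits". None of the three mentions a FLEET CAP score.

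**The same population in Section 3.2.1.** Here the primary population is "subjects who meet the case definition of coccidioidomycosis pneumonia and who were adherent to the intervention administration". The text refers to Section 11.4.1 but sets no condition on serology at particular visits.

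**Case definition, Section 3.2.1.** Criterion 1 is "The patient is positive for any two serologic tests at any time point from Day 1 through Day 29", and the two positives may come from one assay or one time point. Criteria 2 to 4 look for seroconversion or a titer rise after Day 1 and up to Day 29 ("at any time point after Day 1 through Day 29" is the wording of criteria 2 and 4). Day 29 serology is scheduled for everyone (Sections 7.3.2 and 8.2.2.1).

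**Endpoint and coding.** Response is a reduction of at least 50% in FLEET CAP from baseline, so it needs a Day 1 and a Day 22 score. Section 11.4.4.1 says: "Subjects without a clinical response at Day 22 will be coded as treatment failures". It gives no rule for an absent score. Section 11.2.1 speaks in passing of 200 cocci-positive subjects followed to Day 22 for the primary analysis, but the population definition does not contain that condition.

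**The concern.** Entry to the primary set should depend on what the primary analysis needs: case status, adherence and a measured endpoint. The definition instead depends on one particular serum. A subject for whom all three are known is excluded if the Day 22 blood was refused, lost or unusable. A subject whose endpoint is not known is admitted if the blood was drawn. Because Section 3.2.1 describes the same population without the serology clause, two programmers working from this document could build different primary sets.

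The PP count is also what the plan steers by. Section 11.2.1 enrols until 200 subjects are evaluable, and Section 11.3.3 inflates the target if the predicted PP count falls short of 200. Each case excluded for a serum it did not need adds to enrolment. Failures assigned for want of a score would shrink both response rates, and the difference between them, in an analysis apparently meant for measured subjects.

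**Working it through.** **1. Is the Day 22 serum needed for case status?**

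| Case criterion (Section 3.2.1) | Sera that can satisfy it without Day 22 |
|---|---|
| 1: any two positive tests, Day 1 to Day 29 | Day 1 alone, Day 29 alone, or both |
| 2: negative on Day 1, then seroconversion by Day 29 | Day 1 and Day 29 |
| 3: CF negative or indeterminate on Day 1, then titer of at least 2 by Day 29 | Day 1 and Day 29 |
| 4: CF positive on Day 1, then titer rise by Day 29 | Day 1 and Day 29 |

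Every criterion can be met without it.

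**2. The plan's own power.** Inputs from Section 11.2.1: 100 per arm, 0.20 against 0.40, two-sided 0.05, Z test with unpooled variance.

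- SE = √[(0.20×0.80 + 0.40×0.60)/100] = √0.0040 = 0.0632.
- Power = Φ(0.20/0.0632 − 1.96) = Φ(1.20) = 88.5%; the other tail is negligible. The plan states 88%.
- With pooled variance the figure is 87.6%, the entry in Table 5.
- The same unpooled formula gives 85.4% for the mITT case (0.16 against 0.32, 125 per arm), where the plan states 85%.

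The stated figures reproduce.

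**3. Measured cases excluded for want of a Day 22 serum.** The plan enrols until 200 are evaluable, so the cost is enrolment. At the 20% yield of Section 11.2.3, one case costs 1/0.20 = 5 enrolments. The documents give no rate of unusable sera. If it were 5% of otherwise eligible cases (assumed), that is 0.05 × 200 = 10 cases, or 10 × 5 = 50 enrolments.

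**4. Missing scores coded as failures (literal reading of Section 11.4.4.1).** Let a share m of adherent cases in each arm have no Day 22 score, with 100 per arm kept. The rates become 0.20(1−m) and 0.40(1−m). The documents do not give m, so these values are assumptions.

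| m | Rates | Difference | Power (unpooled) |
|---|---|---|---|
| 0 | 0.200 / 0.400 | 0.200 | 88.5% |
| 2% | 0.196 / 0.392 | 0.196 | 87.6% |
| 5% | 0.190 / 0.380 | 0.190 | 86.1% |
| 10% | 0.180 / 0.360 | 0.180 | 83.3% |

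For m = 5%: SE = √[(0.19×0.81 + 0.38×0.62)/100] = 0.0624, and Φ(0.19/0.0624 − 1.96) = Φ(1.08) = 86.1%. The 87.6% at m = 2% matches the Table 5 entry only by coincidence.

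**5. After the fix.** With 100 measured subjects per arm, power is the 88.5% of step 2. The target of 200/0.20 = 1,000 also stands, if the 20% yield is read as measured subjects.

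**The case against.** **Intent.** A reader might infer that the plan codes unmeasured cases as failures. It does not say so. Section 11.4.4.1 never mentions a missing score. Where the plan wants drop-outs imputed it says so, for the cocci-positive mITT and the ITT analyses in Section 11.2.1. The mention of Day 22 follow-up for the primary set points to measured subjects. The literal reading is open only because the definition omits the condition. Section 11.4.4 also defers details to a separate statistical analysis plan, which is not among the documents reviewed and may contain a rule.

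**Power.** A reader might also infer that lost sera reduce power. The documents do not support that. The 20% yield in Section 11.2.3 is already stated as the share eligible for the PP set, and Sections 11.2.1 and 11.3.3 enrol until 200 are evaluable. The cost is further enrolment.

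**Numbers affected.** FLEET CAP, pill count and blood draw are all scheduled at the Day 22 visit (Section 7.3.1). The serology clause therefore works largely as a marker of attendance, and only subjects with one item and not the other are affected. This stands, and it keeps the point small.

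**Uses of the clause.** Three of the six criteria of the alternative case definition (Table 4) need positivity at both Day 22 and Day 29. That definition carries its own visit requirements, however, so the primary set need not carry them for it. A common minimum of sera might give subjects a more equal chance of being classed as cases, but the clause does not require the Day 29 serum, and the cocci-positive mITT has no serology-visit condition at all. Using one clause in both PP sets keeps the cocci-positive set nested in the all-randomized set; so would a common score condition.

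**SO 6.** Its wording, "with baseline and follow-up FLEET-CAP scores", shows that the plan elsewhere names the score as the relevant datum. The analysis attached to it is an ITT analysis with imputation, so it does not define PP evaluability and is weak support.

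**Excluded cases.** They remain in the cocci-positive mITT under SO 1. That is true, but the primary analysis still loses them.

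**Conclusion.** The point holds as a defect of definition. A stated rule removes adherent, confirmed cases with a measured endpoint from the primary analysis; Section 3.2.1 describes the same population without that rule; and the score that the endpoint needs is not an entry condition.

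The size is modest. Each case excluded for its serum costs about five enrolments, assuming the 20% yield. If missing scores were in fact coded as failures, 2% to 5% missing in both arms would cost about 1 to 2.5 points of power. Neither rate is in the documents, and both are probably low because the items share a visit. No stated power or sample size is wrong. This is a cheap improvement to the definition of the primary population.

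**What to change.** Reconcile Sections 3.2.1, 11.2.1, 11.4.1 and 11.4.4.1 by replacing the Day 1 and Day 22 serology clause:

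- **Cocci Positive PP:** compliant subjects who *meet the case definition on serology available through Day 29 and have FLEET CAP scores at Day 1 and at the Day 22 visit*.
- **All Randomized PP:** compliant subjects who *have FLEET CAP scores at Day 1 and at the Day 22 visit*, with no serology condition.
- **Cases without a Day 22 score** stay in the cocci-positive mITT as non-responders. This extends the drop-out rule of Section 11.2.1 to a case who attended but was not scored. Section 11.4.4.1 should then say that its failure coding in the PP set applies to measured subjects.

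The cost is two sentences in the population definitions, with matching wording in the other sections. The one small downside is that a few cases will be classified on fewer sera.
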